Blood pressure and pulse will be taken after the patient has been resting quietly in supine position for 5 minutes. Vital signs assessments during the double-blind phase should occur prior to the post-dose PK sample, and after the ECG assessments.

Physical Examination

Physical examinations, height, and weight will be performed at the times specified in the Time and Events Schedule.

Any abnormalities present at Baseline, or subsequent changes, will be documented in the appropriate sections of the CRF. Any clinically significant abnormalities persisting at the end of the study will be followed by the investigator until resolution or until reaching a clinically stable endpoint.

Columbia Suicide Severity Rating Scale (C-SSRS)

Emergence of suicidal ideation will be assessed using the C-SSRS, a prospective rating scale that tracks both treatment-emergent suicidal ideation and behaviors, and will be

performed at the times specified in the [Time and Events Schedule](#). The C-SSRS has been used frequently in clinical studies, is a standard measure for suicidal ideation assessment, and its use is in accordance with FDA guidance.

See [Attachment 11](#) for an example of this scale.

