10.8.6.1. Columbia Suicide Severity Rating Scale (C-SSRS)

Results from the C-SSRS will be tabulated by treatment.

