ATTACHMENT 10: DIGIT SYMBOL SUBSTITUTION TEST (DSST)

Sample Sheet

Digit symbol substitution test

1	2	3	4	5	6	7	8	9
↔	↓	≡		≠	□	Φ	∈	≅

2	9	2	9	4	9	4	9	1	8	9	3	1	7	2	3	6	4	8	3	1	7	8	2	5
4	7	1	7	5	8	4	1	5	2	6	9	9	5	6	7	6	2	9	4	8	7	2	8	6
8	6	2	8	2	9	4	7	4	8	6	7	3	1	6	2	1	8	7	4	3	1	6	2	9
2	5	4	6	1	6	3	1	2	7	2	6	4	9	1	8	5	7	1	5	4	5	3	9	2
3	9	7	1	7	1	3	5	7	6	1	6	5	9	1	3	1	3	9	8	9	7	3	4	3

**ATTACHMENT 11: COLUMBIA SUICIDE SEVERITY RATING SCALE
(C-SSRS)**

Disclaimer:

This scale is intended to be used by individuals who have received training in its administration. The questions contained in the Columbia-Suicide Severity Rating Scale are suggested probes. Ultimately, the determination of the presence of suicidal ideation or behavior depends on the judgment of the individual administering the scale.

SUICIDAL BEHAVIOR (Check all that apply, so long as these are separate events; must ask about all types)	Since Last Visit

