5.4.2. Clinical Laboratory Assessments

Descriptive summaries of selected (quantitative) clinical laboratory results and change from baseline will be presented by treatment group and visit. Laboratory abnormalities will be determined using pre-defined normal ranges. The number and percentage of patients experiencing TE clinically significant (CS) laboratory abnormalities as reported by the central laboratory, and potentially clinically significant (PCS) abnormalities for select parameters per the table below will be summarized by treatment group. Additionally, shifts in Laboratory values with reference to the normal range from Study Baseline to Week 6 will be summarized by treatment group.

Listings will be provided for patients with any laboratory results outside the reference ranges, as well as for patients with any CS and PCS (select parameters) laboratory results.

Criteria for Potentially Clinically Significant Laboratory Tests

Laboratory Parameter	SI Units	Conversion Factor^a	Traditional Units	PCS Criteria^b Low Values	PCS Criteria^b High Values
Hematology					
Hemoglobin	F	g/L	0.1	g/dL	< 100
	Male				< 120
Hematocrit	F	ratio	100	%	≤ 32% and ≥3% decrease from baseline
	Male				≤ 37% and ≥3% decrease from baseline
White cell count		10 ⁹ /L	1	10 ³ /μL	≤ 2.5
Eosinophils absolute cell count		10 ⁹ /L	1	10 ³ /μL	—
Neutrophils absolute cell count		10 ⁹ /L	1	10 ³ /μL	≤ 1.50
					≥ 15
					≥ 1.50
					≥ 12.0

Lymphocyte absolute cell count	10 ⁹ /L	1	10 ³ /μL	≤ 0.8	≥ 4.0
Platelet count	10 ⁹ /L	1	10 ³ /μL	≤ 75	≥ 700
Chemistry					
Albumin	g/L	0.1	g/dL	< 28	—
Alkaline phosphatase	U/L	1	U/L	—	≥ 2 × UNL
ALT	U/L	1	U/L	—	≥ 3 × UNL
AST	U/L	1	U/L	—	≥ 3 × UNL
Blood urea nitrogen	mmol/L	2.8011	mg/dL	—	> 1.4 × UNL
Calcium	mmol/L	4.008	mg/dL	< 1.97	> 2.77
Cholesterol	mmol/L	38.6698	mg/dL	—	> 7.75
Creatinine	μmol/L	0.0113	mg/dL	—	> 1.4 × UNL
Glucose, fasting	mmol/L	18.015	mg/dL	< 3.0	> 7.6 × UNL
Potassium	mmol/L	1	mEq/L	< 3.3	> 5.5
Sodium	mmol/L	1	mEq/L	< 130	> 150
Total bilirubin	μmol/L	0.0585	mg/dL	—	> 1.5 × UNL
Urinalysis					
Protein	—	—	—	—	≥ 2 +
Glucose	—	—	—	—	≥ 1 +

^a Conversion factor is the multiplication factor to convert from SI units to traditional units.

^b Criteria refer to SI units.

LNL = lower normal limit of laboratory reference range; PCS = potentially clinically significant; SI = *Le Système International d'Unités* (International System of Units); UNL = upper normal limit of laboratory reference range.

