5.4.4. Other Safety Analyses

Descriptive summaries of vital signs data including body temperature, pulse, respiratory rate, and blood pressure (systolic and diastolic) and respective changes from Baseline, will be presented by time point and treatment group. The number and percentage of patients with PCS vital signs per the table below, as determined in the eCRF, occurring post-baseline will

also be summarized by time point and treatment group. All vital signs will be listed with clinically significant values flagged, as well as for patients with any PCS results.

CRITERIA FOR POTENTIALLY CLINICALLY SIGNIFICANT VITAL SIGNS

Parameter	Flag	Criteria
		Observed Value
Systolic blood pressure (mm Hg)	High	≥ 150
	Low	≤ 90
Diastolic blood pressure (mm Hg)	High	≥ 100
	Low	≤ 50
Pulse rate (bpm)	High	≥ 110
	Low	≤ 50
Temperature (°C)	High	≥ 38
	Low	< 35

Electrocardiogram (ECG) variables and their change from baseline will be summarized with descriptive statistics by time point and treatment group. ECG variables will include heart rate, PR interval, QRS interval, QT interval, and QTc interval corrected for heart rate using QTcF. QTcF values will also be tabulated for their absolute values and tabulated relative to baseline measurements in order to detect individual QTcF changes. Additionally, the number and percentage of patients with PCS values defined in the table below

Use header of the convention table for all relevant safety parameters.

Criteria for Potentially Clinically Significant ECG Parameters

Parameter	Flag	Criteria	
		Observed Value	Change from Baseline or Observed Value
Heart Rate (bpm)	High	> 110	
	Low	≤ 50	

QTcF ^a Interval (msec)	High Male	> 450	30-60, > 60, > 500
	High Female	> 470	
QRS Interval (msec)	High	> 120	
PR Interval (msec)	High	> 220	

^a QTc interval (Fridericia's) is derived as: $QTcF = QT \text{ Interval (msec)} / (RR \text{ (msec)/1000})^{1/3}$

For these summaries, worst-case assignments will be made to ensure patients with such values are not counted more than once. For example, a patient with QTcF interval > 500 msec will count once in the > 500 msec category and will not appear in the > 450 or > 480 msec categories. Similar conventions will be used for the 30 to 60 and > 60 msec categories. All ECG analyses will be based on the average of triplicate measurements.

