Important abnormalities in ECG waveform that are changes from Baseline readings will also be reported in a listing. All ECG will be listed with clinically significant values flagged, as well as for patients with any PCS results.

All physical examination results will be listed.

Results from the Columbia-Suicide Severity Rating Scale (C-SSRS) will be summarized by visit and treatment group. All C-SSRS results will also be reported in a listing.

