 - 14.3.1.5 Treatment-Emergent Fatal Adverse Events by System Organ Classification and Preferred Term, Safety Population
 - 14.3.2.1 Treatment-Emergent Serious Adverse Events by System Organ Classification and Preferred Term, Safety Population
 - 14.3.4.1 Clinical Laboratory Hematology Parameters by Time Point, Safety Population
 - 14.3.4.2 Clinical Laboratory Chemistry Parameters by Time Point, Safety Population
 - 14.3.4.3.1 Clinically Significant Laboratory Values, Safety Population
 - 14.3.4.3.2 Clinically Significant and Potentially Clinically Significant Laboratory Values, Safety Population
 - 14.3.4.4 Clinical Laboratory Parameter Shifts from Study Baseline to Week 6, Safety Population
 - 14.3.5.1 Vital Signs by Time Point, Safety Population
 - 14.3.5.2.1 Patients with Clinically Significant Vital Signs Occurring Post-Baseline, Safety Population
 - 14.3.5.2.2 Patients with Clinically Significant or Potentially Clinically Significant Vital Signs Occurring Post-Baseline, Safety Population
 - 14.3.5.3.1 12-Lead ECG Assessments by Time Point, Safety Population
 - 14.3.5.3.2 Summary of QTcF (msec) Categories, Safety Population
 - 14.3.5.4 Patients with Significant ECG Abnormalities Occurring Post-Baseline, Safety Population
 - 14.3.6.1 Summary of C-SSRS by Visit, Safety Population

Data Listings

- 16.2.1 Patient Disposition
 - 16.2.2.1 Protocol Deviations
 - 16.2.2.2 Inclusion/Exclusion Criteria
 - 16.2.4.1 Demographics
 - 16.2.4.2 Medical and Surgical History
 - 16.2.5.1 Study Drug Administration
 - 16.2.5.2 Prior and Concomitant Medications
 - 16.2.5.3.1 Pharmacokinetic Plasma Concentrations
 - 16.2.6.1 MADRS Rating Scale
 - 16.2.6.2 CGI-S and CGI-I Questionnaires
 - 16.2.6.3 HAM-A Questionnaires
 - 16.2.6.4 IDS-SR₃₀ Questionnaires
 - 16.2.6.5 SHAPS Questionnaires
 - 16.2.6.6 DSST Questionnaires
 - 16.2.6.7 PSS Questionnaires
 - 16.2.6.8 A-SEX Questionnaires
 - 16.2.6.9 C-SSRS Questionnaires
-

16.2.6.10	Somno-Art Sleep Parameters
16.2.7	Adverse Events
16.2.8.1.1	Laboratory Data – Chemistry
16.2.8.1.2	Laboratory Data – Hematology
16.2.8.1.3	Laboratory Data – Urinalysis
16.2.8.1.4	Laboratory Data – Other
16.2.8.1.5	Laboratory Results Outside Reference Range
16.2.8.1.6	Potentially Clinically Significant Laboratory Results
16.2.8.2.1	Vital Signs
16.2.8.2.2	Weight, Height and BMI
16.2.8.3	Physical Examinations
16.2.8.4	12-Lead ECG Findings

Figures

14.2.1.1.5	Change from Baseline in MADRS by Visit, ITT Population

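### The SAP summarises the C-SSRS only by visit and arm, so no planned summary counts the patients with treatment-emergent suicidal ideation or behaviour

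*SAP*

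**What the plan says.** - **Purpose.** Protocol 8.6 states: "Emergence of suicidal ideation will be assessed using the C-SSRS, a prospective rating scale that tracks both treatment-emergent suicidal ideation and behaviors".
- **Collection.** The Time and Events Schedule has the C-SSRS at Screening, Baseline, Weeks 2, 4 and 6 (or early withdrawal), and the Week 8 follow-up. That is four scheduled assessments after Baseline.
- **Protocol analysis.** Section 10.8.6.1 says only: "Results from the C-SSRS will be tabulated by treatment".
- **SAP analysis.** Section 5.4.4 says: "Results from the Columbia-Suicide Severity Rating Scale (C-SSRS) will be summarized by visit and treatment group". It adds: "All C-SSRS results will also be reported in a listing".
- **Planned outputs.** SAP section 9 has one C-SSRS table, 14.3.6.1, titled "Summary of C-SSRS by Visit, Safety Population", and listing 16.2.6.9.
- **Which assessments reach a by-visit table.** SAP 3.3.7 assigns unscheduled and early-termination assessments to a visit window only when the scheduled visit did not take place. The first window is Days 9 to 22. Where a time point has several results, the one closest to the target day is used, and a tie goes to the earlier.
- **Other safety data.** SAP 5.4.2 plans for laboratory data: "The number and percentage of patients experiencing TE clinically significant (CS) laboratory abnormalities as reported by the central laboratory", together with shifts from Baseline to Week 6. For ECG categories, SAP 5.4.4 says "worst-case assignments will be made to ensure patients with such values are not counted more than once".

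Neither document defines emergent or worsened ideation or behaviour on the C-SSRS, a worst post-dose category, a shift table, or a once-per-patient count.

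**The concern.** The protocol gives the scale a patient-level purpose: who developed suicidal ideation or behaviour after starting treatment. The only planned summary is a series of visit-level counts. For ideation, a visit-level count mixes patients who already had it before dosing with patients in whom it is new, and it does not show whether the positives at one visit are the same people as at the next. Eligibility excludes patients at significant clinical risk of suicidal behaviour, but it does not exclude all pre-dose ideation, so the distinction matters.

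Safety is a secondary objective, and this is an investigational antidepressant in moderate to severe MDD. The number of patients per arm with emergent suicidality is a result that readers will look for. As planned, it would have to be worked out from the listing, with the definition and pre-dose reference chosen after unblinding.

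**Working it through.** The documents state no figure for the C-SSRS, so there is nothing to reproduce. The check is whether the planned table determines the number of interest.

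**Inputs.** Four post-Baseline assessments (Time and Events Schedule). 81 patients per MIN-117 arm (SAP 3.1). The per-visit share p is an assumption, shown over a range.

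**Step 1: bounds.** Let N patients be assessed at every visit, with pN positive at each of four post-Baseline visits.
- Patients ever positive: at least pN (the same patients each time), at most 4pN (different patients each time).
- Emergent patients: at most 4pN, and possibly 0 if every positive patient was already positive at Baseline and did not worsen.

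| Assumed p | Lowest ever-positive share (p) | If visits were independent, 1 − (1 − p)^4 | Highest (4p) |
|---|---|---|---|
| 2% | 2% | 7.8% | 8% |
| 3% | 3% | 11.5% | 12% |
| 5% | 5% | 18.5% | 20% |

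**Step 2: illustration with assumed counts, not trial data.** Take 81 patients, with 3 positive at Baseline and 3 at each of the four later assessments.
- If the same 3 patients are positive throughout, with no worsening, 0 of 81 are emergent.
- If different patients are positive at each time point, 4 × 3 = 12 of 81 are emergent, or 14.8%. The 3 Baseline positives are separate: 3 + 12 = 15 patients ever positive.
- The by-visit row is 3, 3, 3, 3, 3 in both cases.

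If the table is split by ideation category, the same bounds apply to the row for each category or worse. The finer table shows a change in the mix of severity, but still not how many patients worsened.

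**Step 3: ideation and behaviour differ.** The behaviour part of the form in Protocol Attachment 11 is headed "Since Last Visit". A positive post-dose behaviour entry is therefore a new occurrence in that interval. For behaviour, the table's limit is narrower: a patient positive at two visits appears twice, so the number of patients with any post-dose behaviour again lies between p and 4p of the arm.

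**Step 4: assessments left out of the table (SAP 3.3.7).**
- A patient who stops on Day 6: the early-termination C-SSRS falls before Day 9 and fits no window.
- A patient seen for Week 2 on Day 15 who stops on Day 20: Day 20 lies in the Day 9 to 22 window, but the scheduled visit was performed, so the Day 20 result is not used.
- An unscheduled C-SSRS between two completed visits is likewise not used, even if it is the patient's worst.

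All three appear in the listing only.

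**The case against.** The strongest reply has four parts.

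1. **The data are reported.** Every C-SSRS result is listed, and with about 324 patients emergent cases can be found by hand. This stands: a reader might infer that emergent cases would go unreported, and that is wrong. What is missing is a summary with a definition fixed in advance.
2. **Other outputs bear on suicidality.** Suicidality recorded as an adverse event enters the TEAE tables, where repeated events under one preferred term are collapsed per patient, with separate serious and fatal tables. The MADRS suicidal-thoughts item (item 10) is among the single items whose change from Baseline is summarised by visit and compared at Week 6. Both are real backstops, but partial. The first depends on the investigator recording an event. The second describes change in scores and does not count patients. It is not collected at follow-up, and Attachment 2 says attempts should not in themselves affect the rating.
3. **The SAP keeps the protocol's analysis commitment.** Protocol 10.8.6.1 promises only a tabulation by treatment, which the SAP provides. A reader might infer a breach of the protocol from section 8.6, but that section states what the instrument is for and does not prescribe an analysis. The point is a mismatch between purpose and summary.
4. **No harm is shown.** A reader might infer that the table will look balanced or improving while emergent cases differ by arm. The documents give no ideation rates and no statement that ideation falls over time, so they do not support a prediction. They support only that the table could not rule this out. The added table would also rest on few events. With hypothetical counts of 5 of 81 against 5 of 162, the ratio is (5/81)/(5/162) = 2.0. The standard error of its logarithm is √(1/5 − 1/81 + 1/5 − 1/162) = 0.62, giving a 95% interval of about 0.6 to 6.7.

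**Conclusion.** The point holds in a limited form. The SAP plans one by-visit C-SSRS table and a listing, with no per-patient summary of treatment-emergent ideation or behaviour. The by-visit table cannot yield that number: the ever-positive share is known only to within a factor of four, and the emergent count in the illustration runs from 0 to 12 of 81. The bounds assume equal prevalence at four visits and complete attendance. The values of p and the counts of 3 are assumptions.

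The windowing rule adds a smaller problem, since some post-dose assessments reach only the listing. How many cannot be known in advance.

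The argument about persisting cases applies to ideation. For behaviour, the issue is repeat counting across visits. The ideation items and the pre-dose version of the form could not be checked here, so nothing is concluded about their categories or recall periods.

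The primary analysis and sample size are unaffected. This is a worthwhile and inexpensive improvement to a descriptive safety analysis.

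**What to change.** Add to SAP 5.4.4, before unblinding:

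- **Derivation.** For each patient, the worst ideation category and any suicidal behaviour over all assessments after first dose: scheduled, unscheduled, early termination and follow-up. State that the visit selection in SAP 3.3.7 does not apply to these variables.
- **Reference.** State the pre-dose reference. It can be the SAP Baseline (SAP 3.3.8, the last valid evaluation before dosing on Day 1), or the worse of Screening and Baseline. The second departs from the SAP definition. If the Screening form has a longer recall, it could classify a recurrence as not new, so the recall period must be stated.
- **Table.** By arm, the shift from the reference category to the worst post-dose category, with the number and percentage of patients with new or worsened ideation and with any post-dose behaviour. Count each patient once.

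Keep table 14.3.6.1 and listing 16.2.6.9, and add the new table to SAP section 9.

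The cost is one set of derived variables and one table from data already collected. The table should be presented as descriptive, because it will probably rest on few events.

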6. PROTOCOL VIOLATIONS

Possible protocol deviations will be identified and displayed in a data listing and sorted by patient and study day (where applicable). The following deviations may be identified as protocol deviations from the database:

- Violations of inclusion/exclusion criteria
- Non-compliance with MIN-117

7. CHANGES IN THE PLANNED ANALYSES

No deviations in the conduct of the study or the planned analysis are anticipated. Should any deviations from the analyses specified in the authorized statistical analysis plan arise, such deviations will be documented in the final clinical study report.

8. PROGRAMMING CONVENTIONS

- Page orientation, margins, and fonts: Summary tables, listings, and figures will appear in landscape orientation. There should be a minimum of a 1.25” boundary on the upper (bound) edge, and a minimum of a 1.0” boundary on the remaining three edges. Output should be printed in Courier New with a point size of 8. Titles may be printed using a larger font (e.g., Arial point size 10).
 - Identification of analysis population: Every summary table and figure should clearly specify the analysis population being summarized. Listings will be prepared for all patients.
 - Group headers: In the summary tables, the group headers will identify the summary group and the sample size for the indicated analysis population. Of note, the header’s sample size does not necessarily equal the number of patients actually summarized within any given summary module; some patients in the analysis population may have missing values and thus may not be summarized.
 - Suppression of percentages corresponding to null categories: When count data are presented as category frequencies and corresponding percentages, the percent should be suppressed when the count is zero in order to draw attention to the non-zero counts.
 - Presentation of sample sizes: Summary modules should indicate, in one way or another, the number of patients actually contributing to the summary statistics presented in any given summary module. As mentioned above, this may be less than the number of patients in the analysis population due to missing data.
 - ◆ In the quantitative modules describing continuous variables (and thus presenting sample size, means, and standard deviations), the sample size should be the number of non-missing observations. The number of missing observations, if any, will be noted.
 - ◆ For categorical variables that are presented in frequency tables, the module should present the total count in addition to the count in each category. Percentages should be calculated using this total as the denominator, and the percentage corresponding to the sum itself (that is, 100%) should be presented so as to indicate clearly to a reviewer the method of calculation. The number of missing observations, if any, will be noted.
 - Sorting: Listings will be sorted by treatment group, patient number and date, if applicable. If a listing is sorted in a different manner, a footnote will indicate as such.
 - General formatting rules: Rounding for all variables will occur only as the last step, immediately prior to presentation in listings, tables, and figures. No intermediate
-

rounding will be performed on derived variables. The standard rounding practice of rounding numbers ending in 0-4 down and numbers ending in 5-9 up will be employed.

- The presentation of numerical values will adhere to the following guidelines:
 - ◆ Raw measurements will be reported to the number of significant digits as captured electronically or on the CRFs.
 - ◆ Standard deviations will be reported to one decimal place beyond the number of decimal places the original parameter is presented.
 - ◆ Means will be reported to the same number of significant digits as the parameter.
- Dates will be formatted as DDMMYYYY. Partial dates will be presented on data listings as recorded on CRFs.
 - ◆ Time will be presented according to the 24-hour clock (HH:MM).

9. PROPOSED TABLES, LISTINGS, AND FIGURES

Summary Tables

Accountability and Baseline Characteristics

- 14.1.1 Final Patient Disposition, All Enrolled Patients
- 14.1.2.1 Demographics, Safety Population
- 14.1.2.2 Baseline Disease Characteristics, Safety Population
- 14.1.3 Drug Exposure and Compliance, Safety Population
- 14.1.4 Concomitant Medications by ATC Classification and Preferred Term, Safety Population

Efficacy

- 14.2.1.1.1 Summary of MADRS Total Score by Visit, ITT Population
- 14.2.1.1.2 Summary of MADRS Total Score by Visit – Sensitivity with LOCF, ITT Population
- 14.2.1.1.3 Summary of MADRS Total Score by Visit – Sensitivity with LOCF and Placebo Average, ITT Population
- 14.2.1.1.4 Summary of MADRS Total Score – Sensitivity with Multiple Imputation, ITT Population
- 14.2.2.1.1 Summary of HAM-A Score by Visit, ITT Population
- 14.2.2.1.2 Summary of HAM-A Score by Visit – Sensitivity with LOCF, ITT Population
- 14.2.2.1.3 Summary of HAM-A Score by Visit – Sensitivity with LOCF and Placebo Average, ITT Population
- 14.2.2.1.4 Summary of HAM-A Score– Sensitivity with Multiple Imputation, ITT Population
- 14.2.2.2 Summary of CGI-S and CGI-I Score by Visit, ITT Population
- 14.2.2.3 Summary of IDS-SR₃₀ Score by Visit, ITT Population
- 14.2.2.4 Summary of SHAPS Score by Visit, ITT Population
- 14.2.2.5 Summary of DSST Score by Visit, ITT Population
- 14.2.2.6 Summary of PSS Score by Visit, ITT Population
- 14.2.2.7 Summary of A-SEX Score by Visit, ITT Population
- 14.2.3.1 MADRS Response by Visit, ITT Population
- 14.2.3.2 Remission and Sustained Response in MADRS, ITT Population
- 14.2.3.3 Time to MADRS Improvement, ITT Population
- 14.2.3.4 Summary of Single MADRS Rating Scale Items by Visit, ITT Population
- 14.2.3.5 Summary of MADRS Core Mood Items by Visit, ITT Population
- 14.2.4.1 Summary of Sleep Parameters by Visit, ITT Population

Safety

- 14.3.1.1 Overall Summary of Treatment-Emergent Adverse Events, Safety Population
- 14.3.1.2 Treatment-Emergent Adverse Events by System Organ Classification, Preferred Term and Maximum Severity, Safety Population
- 14.3.1.3 Treatment-Emergent Adverse Events Related to Study Treatment by System Organ Classification, Preferred Term and Maximum Severity, Safety Population

-
- 14.3.1.4 Treatment-Emergent Adverse Events Leading to Discontinuation of Study Treatment by System Organ Classification, Preferred Term and Maximum Severity, Safety Population
 - 14.3.1.5 Treatment-Emergent Fatal Adverse Events by System Organ Classification and Preferred Term, Safety Population
 - 14.3.2.1 Treatment-Emergent Serious Adverse Events by System Organ Classification and Preferred Term, Safety Population
 - 14.3.4.1 Clinical Laboratory Hematology Parameters by Time Point, Safety Population
 - 14.3.4.2 Clinical Laboratory Chemistry Parameters by Time Point, Safety Population
 - 14.3.4.3.1 Clinically Significant Laboratory Values, Safety Population
 - 14.3.4.3.2 Clinically Significant and Potentially Clinically Significant Laboratory Values, Safety Population
 - 14.3.4.4 Clinical Laboratory Parameter Shifts from Study Baseline to Week 6, Safety Population
 - 14.3.5.1 Vital Signs by Time Point, Safety Population
 - 14.3.5.2.1 Patients with Clinically Significant Vital Signs Occurring Post-Baseline, Safety Population
 - 14.3.5.2.2 Patients with Clinically Significant or Potentially Clinically Significant Vital Signs Occurring Post-Baseline, Safety Population
 - 14.3.5.3.1 12-Lead ECG Assessments by Time Point, Safety Population
 - 14.3.5.3.2 Summary of QTcF (msec) Categories, Safety Population
 - 14.3.5.4 Patients with Significant ECG Abnormalities Occurring Post-Baseline, Safety Population
 - 14.3.6.1 Summary of C-SSRS by Visit, Safety Population

Data Listings

- 16.2.1 Patient Disposition
 - 16.2.2.1 Protocol Deviations
 - 16.2.2.2 Inclusion/Exclusion Criteria
 - 16.2.4.1 Demographics
 - 16.2.4.2 Medical and Surgical History
 - 16.2.5.1 Study Drug Administration
 - 16.2.5.2 Prior and Concomitant Medications
 - 16.2.5.3.1 Pharmacokinetic Plasma Concentrations
 - 16.2.6.1 MADRS Rating Scale
 - 16.2.6.2 CGI-S and CGI-I Questionnaires
 - 16.2.6.3 HAM-A Questionnaires
 - 16.2.6.4 IDS-SR₃₀ Questionnaires
 - 16.2.6.5 SHAPS Questionnaires
 - 16.2.6.6 DSST Questionnaires
 - 16.2.6.7 PSS Questionnaires
 - 16.2.6.8 A-SEX Questionnaires
 - 16.2.6.9 C-SSRS Questionnaires
-

16.2.6.10	Somno-Art Sleep Parameters
16.2.7	Adverse Events
16.2.8.1.1	Laboratory Data – Chemistry
16.2.8.1.2	Laboratory Data – Hematology
16.2.8.1.3	Laboratory Data – Urinalysis
16.2.8.1.4	Laboratory Data – Other
16.2.8.1.5	Laboratory Results Outside Reference Range
16.2.8.1.6	Potentially Clinically Significant Laboratory Results
16.2.8.2.1	Vital Signs
16.2.8.2.2	Weight, Height and BMI
16.2.8.3	Physical Examinations
16.2.8.4	12-Lead ECG Findings

Figures

14.2.1.1.5	Change from Baseline in MADRS by Visit, ITT Population
14.2.2.1.5	Change from Baseline in HAM-A by Visit, ITT Population
14.2.3.6	Change from Baseline in Single MADRS Rating Scale Items by Visit, ITT Population
14.2.3.7	Time to $\geq 50\%$ MADRS Improvement, ITT Population
14.2.3.8	Time to $\geq 30\%$ MADRS Improvement, ITT Population
